**Safety and Monitoring:**

1. **Comfort:** Subjects will be asked to verbally rate (1-5 scale) severity, location and quality (self described) of any discomfort immediately prior to the scan, after each block during the scans, immediately after the stimulation session and at 10 minutes after the stimulation sessions. If any discomfort persists at 10 minutes after stimulation, treatment and ongoing assessment will be arranged as needed by the study physician.

2. **Cognitive Effects:** Baseline memory, attention and verbal reasoning will be assessed using the Digits span test from the WASI, which assesses short-term memory and attention. This will be repeated 10 minutes after the stimulation. Subjects will also be asked open ended questions about any changes in their thinking or cognitive status. Research staff will follow up with participants in the second and third sessions and 5 to 14 days after the third session to query the persistence or emergence of any cognitive changes.

3. **Psychiatric Effects:** Emotional, motivational and behavioral symptoms will be assessed using the PANAS (Positive and Negative Affect Scale) before stimulation and immediately following stimulation.

**Phase 3. Neural effects on behavior.** In Phase 3, we will test the effectiveness of Temporal Interference-NDBS on reducing smoking and cigarette craving in heavy smokers. To test this, we will proceed with two stages. In the first stage (pilot), we will recruit heavy smokers into three groups, then ask them to abstain from smoking. One group will receive TI-NDBS to the left and

right insula. Another group will receive TI-NDBS over the nucleus accumbens. Another group will receive TI-NDBS to the anterior cingulate cortex. We will not target these brain areas in any particular order. Prior to stimulation, subjects will be administered a questionnaire to assess their physical experiences and sensations using a 5-point Likert-scale. Subjects will also be given the Nicotine Dependence Syndrome Scale to assess baseline Nicotine Dependence. In addition, we will measure total real-time ad lib nicotine vapor inhalation during a 60 minute stimulation session. At the start of the stimulation, the current will increase slowly at a constant rate for 30 seconds until it reaches the appropriate intensity. At the end of the stimulation, the current will decrease slowly for 30 seconds until it reaches zero. Every ten minutes, we will ask subjects to self-report their level of craving on a Likert scale of 1-10. We will identify whether TI-NDBS to the insula or nucleus accumbens or cingulate is more effective stimulation at decreasing cravings. In the second stage of Phase 3, we will take the two most promising of the three brain regions and repeat the procedure of stage 1, but with a larger sample size. The third group will receive sham stimulation as a control. In both stages, immediately after stimulation, subjects will complete the stimulation experience scale and then again 30 minutes later. We will then follow up with subjects every day, up to three times per day, for a period of 1 week afterward using Ecological Momentary Assessment (EMA) via a smartphone app (LifeData) to monitor cigarette and/or vaping use and craving. The questions that will be used in the app are in a script attached (see EMA follow up questions). In Phases 1, 2, and 4 subjects are paid \$25/hr. In Phase 3, subjects are paid \$40/hr. In addition, in Phases 3 and 4, subjects are paid \$5/day for providing ecological momentary assessment data outside of the lab sessions, and \$10 bonus for completing 7 consecutive days of ecological momentary assessment (EMA). Payment will be made at the end of each day's lab session in cash, and for phase 3, by check after the EMA period ends.

Additionally, after consenting, subjects in all phases will be asked to fill out a contact form detailing their email address, home address, and phone number, as well as their preferred method of contact. This form will be used to pay subjects via mail as well as contact them for potential participation in future studies if they are interested.

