#### Safety and Monitoring:

- (1) **Comfort:** Subjects will be asked to rate (1-5 scale) severity, location and quality (self described) of any discomfort immediately prior to the stimulation, at 5 and 15 minutes during stimulation, immediately after the stimulation and at 10 minutes after the stimulation. If any discomfort persists at 10 minutes after stimulation, treatment and ongoing assessment will be arranged as needed by the study physician.
- (2) **Cognitive Effects:** Baseline memory, attention and verbal reasoning will be assessed using the Digits span test from the WAIS, which assesses short-term memory and attention. This will be repeated 10 minutes after the stimulation. Subjects will also be asked open ended

questions about any changes in their thinking or cognitive status. Research staff will contact subjects between days 2 and 5 after scanning to query the persistence or emergence of any cognitive changes.

(3) **Psychiatric Effects:** Emotional, motivational and behavioral symptoms will be assessed before stimulation and immediately following stimulation. Subjects will be contacted to follow up between days 2 and 5 after scanning to query the persistence or emergence of any changes to their emotions, motivation or behavior. This testing will involve using the PANAS-SF test of positive and negative affect.

**In the unlikely event of serious adverse events occurring in Phase 1, the study team will report back to the DSMB and the IRB to assess whether or not the study could proceed to Phases 2-4.**

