**Phase 2. Neural effects.** In Phase II, subjects will complete the MRI safety screen questionnaire and the stimulation experience scale (the same scale from phase 1) prior to entering the MR scanner. The electrodes (2 cm x 2 cm) will be attached and subjects will enter the MR scanner and the TI-NDBS stimulation will be administered while in the scanner, alternating 2-minute stimulation and 2-minute no-stimulation periods. Subjects may alternatively receive stimulation from all electrodes at the same frequency in order to make comparisons to temporal interference stimulation. For every two minute period of stimulation, the current will increase slowly at a constant rate for 30 seconds until it reaches the appropriate intensity. At the end of the stimulation, the current will decrease slowly for 30 seconds until it reaches zero. For sham stimulation, the current will increase during a 30 second interval and then immediately decrease back to zero over a 30 second interval, for a total of 60 seconds of stimulation. This will allow us to identify immediate neural activation due to stimulation, while controlling for any scalp sensations with the sham condition. The electrodes will be placed to target stimulation at either anterior Cingulate or nucleus accumbens. Immediately following the stimulation session, subjects will complete the stimulation experience scale and then will clean off residual electrode gel. The stimulation experience scale is administered again 30 minutes later. The subject will be in the scanner for about 1 hour.

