- The device settings are controlled by a separate microcontroller, typically a Raspberry Pi zero, which communicates with the device via serial protocols, namely SPI and I2C. The raspberry pi is a fully functional computer that can be programmed to run timed stimulation protocols and control the neurostimulator.
- The four electrodes will be placed on the subject's scalp (Figure 1) at locations designated in the international 10/20 system, as used for EEG. The locations will be optimized by finite element modeling to target specific brain regions such as the dorsal anterior cingulate cortex (dACC), insular cortex, and nucleus accumbens.
- Should stimulation be terminated early for any reason, the same stimulation assessments will be conducted as if the session lasted the full 40 minutes including the EMA, stimulation experience scale, heart rate, blood pressure, psychiatric symptoms, nicotine craving, etc. The reason for termination will be recorded and an unanticipated event filed with the IRB. If the subject experiences an adverse reaction to the stimulation, this will be recorded and reported to the IRB and DSMB.

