**5.0 Outcome Characteristics and Endpoint Definitions:**

For Phase 1, we will determine if any participants report adverse reactions or any side effects from the TI-NDBS stimulation, using the Stimulation Experience Scale questionnaire. Some potential side effects include itching, unusual sensations, abnormal or unpleasant thoughts, or physical sensations. We will follow-up with participants after the stimulation session to determine if there were any side effects from TI-NDBS. For phase 2, we will measure the change in neural activity for each target area of the brain to be stimulated for TI-NDBS vs. no stimulation to determine if the activity is different for TI-NDBS stimulation, again using the Stimulation Experience Scale. For phase 3, we will determine whether TI-NDBS vs. sham leads to a difference in nicotine craving via self-report measures and corresponding reduced nicotine vapor inhalation in the MRI scanner. For phase 4, we will determine a difference in nicotine craving via self-report measures and corresponding reduced nicotine vapor inhalation in the MRI scanner between TI-NDBS and tDCS. We will also examine differences in neural activity measured by fMRI between TI-NDBS and tDCS.

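### Phase 2 drops Phase 1's delayed question on emotions, motivation or behavior, and its final safety contact has no date for a subject who stops before session 3

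*Combined protocol and SAP*

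**What the plan says.** **Phase 2 (3.0 Design, Phase 2, Safety and Monitoring).** Under Cognitive Effects: "Research staff will follow up with participants in the second and third sessions and 5 to 14 days after the third session", the purpose being "to query the persistence or emergence of any cognitive changes". Under Psychiatric Effects, the PANAS is given "before stimulation and immediately following stimulation", and no later contact is mentioned. Under Comfort, the study physician arranges treatment and further assessment if discomfort is still present 10 minutes after stimulation. The Phase 2 description adds a same-day check: "The stimulation experience scale is administered again 30 minutes later".

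**Phase 1 (3.0 Design, Phase 1, Safety and Monitoring).** There are two delayed queries, both between days 2 and 5. One concerns cognition. The other is under Psychiatric Effects: "Subjects will be contacted to follow up between days 2 and 5 after scanning", to ask about "any changes to their emotions, motivation or behavior".

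**Elsewhere.** The TI device section says that when stimulation is ended early, the assessments of a full session are still done (psychiatric symptoms are named), the reason is recorded, and an unanticipated event is filed with the IRB. It adds: "If the subject experiences an adverse reaction to the stimulation, this will be recorded and reported to the IRB and DSMB". Section 5.0 says: "We will follow-up with participants after the stimulation session to determine if there were any side effects from TI-NDBS".

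**The concern.** Phase 2 stimulates the anterior cingulate or the nucleus accumbens. The protocol's Background links the first to loss of voluntary motivation after lesions, and the second to riskier choices under implanted deep brain stimulation. It calls these extreme clinical cases and does not expect them from this device. They are no evidence of harm here, but they show that motivation and behavior are natural things to ask about, and this is the domain in which the delayed question disappears.

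Phase 1 cannot make the question unnecessary. It has 3 subjects and describes a single stimulation session, whereas the Phase 2 safety text implies up to three. Section 7.0 names adverse events as the ground on which the study may be ended early. A change in mood or motivation that appears a day or more after the last session would reach the investigator only if the subject volunteered it.

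The second, smaller matter is timing. Only one Phase 2 contact falls after a subject's final stimulation, and it is dated from session 3. For someone who stops after session 1 or 2 the plan does not say when, or whether, that contact takes place.

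**Working it through.** The plan gives no figure to reproduce. The check is mainly a comparison of text.

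**Step 1: later-day queries in the two phases**

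| | Phase 1 | Phase 2 |
|---|---|---|
| Cognition | Days 2 to 5 | Sessions 2 and 3, and 5 to 14 days after session 3 |
| Emotions, motivation, behavior | Days 2 to 5 | None |
| PANAS | Before and right after stimulation | Before and right after stimulation |

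Phase 1 dates its contacts from scanning although it describes no scan; I read this as the stimulation session. The three-session structure of Phase 2 comes from the safety text, since the Phase 2 description covers one session.

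**Step 2: could another provision supply the missing query?**

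- *TI device section.* It secures the assessments of a full session when a session is cut short, and the reporting of reactions. It adds no later-day contact and does not re-date the final one. Its list includes EMA, but the design text sets up EMA only for Phases 3 and 4, to follow smoking and craving.
- *Section 5.0.* The follow-up sentence stands in the Phase 1 endpoint text, ahead of the Phase 2 sentence, and has no timing.
- *Physician follow-up under Comfort.* It applies at any session, but is triggered by discomfort present at 10 minutes, not by a change that emerges later.
- *PANAS before sessions 2 and 3.* If repeated at each session, it may show some carry-over of affect in subjects who return. It is not a question about motivation or behavior, and none follows the last session.

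**Step 3: who is asked what after the last stimulation day**

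- Completes three sessions: cognition yes; emotions, motivation or behavior no.
- Stops after session 2: asked about cognition at session 2, which looks back to session 1; no dated query after session 2.
- Stops after session 1: no dated later-day query.

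So the number asked about emotions, motivation or behavior is 0 of 10 (n = 10 from section 6.0), whoever stops early.

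**Step 4: what the question would give**

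With no events in n subjects asked, the one-sided 95% upper limit is 1 − 0.05^(1/n).

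- n = 10 (Phase 2, all asked): 1 − 0.05^(1/10) = 0.259, or 26%.
- n = 3 (Phase 1, all asked): 1 − 0.05^(1/3) = 0.632, or 63%.

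A clean Phase 1 result would therefore still be compatible with a high rate. Phase 2 could bring the limit down to 26%, but only if the question is asked.

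**Step 5: burden**

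Three planned contacts for 10 subjects give at most 10 × 3 = 30 added question sets, or at most 10 if the question is added only at the final contact.

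**The case against.** The strongest reply is that the phases differ for good reason. Phase 1 is the first tolerability cohort, with 30 minutes of continuous stimulation and no described return visit, so a delayed contact is its only later look. Phase 2 starts after Phase 1 is complete, uses 2-minute blocks and brings subjects back, when the PANAS and the experience scale would naturally be repeated. For a subject who completes all sessions, the gap narrows to what the PANAS does not measure, plus everything after session 3. That stands, and it limits the size of the point. It does not close the gap, because the final contact is already planned and leaves this domain out.

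The reply also has force on early stopping. The plan does not say that early stoppers are skipped; it only gives no date. Someone who stops because of discomfort may come under physician follow-up, and an early-terminated session is assessed and reported to the IRB. A reader might infer that reactions go unfollowed. The documents do not support that: what is left uncovered is change in mood, motivation or cognition that emerges later.

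A reader might also infer that early stoppers are a selected group and that results at 5 to 14 days would be biased. The documents do not support this either. They give no stopping rate and no reasons for stopping, missed sessions may be a matter of scheduling, and no analysis at 5 to 14 days is planned; the Phase 2 endpoint is neural activity.

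Finally, the protocol's evidence on persistence is mixed. It reports weak, non-persistent changes with tACS directed at the anterior cingulate, and its example of effects beyond 6 months is improved numerical ability after tDCS during learning. Neither suggests lasting mood harm. The case rests on asking, not on an expected harm.

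**Conclusion.** The point holds as an inexpensive safety improvement, not as a flaw that threatens the trial. Followed as written, Phase 2 asks none of its 10 subjects about emotions, motivation or behavior after the day of the last stimulation, although Phase 1 schedules that question. The consequence is the absence of any estimate where 10 clean answers would support an upper limit of 26%.

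The missing date for early stoppers is secondary. It follows from the session-3 anchor together with silence on discontinuation, and is partly covered by existing provisions. I put no number on it and claim no bias from it.

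The conclusion assumes that the Phase 2 safety text is the full list of later-day queries, and that the section 5.0 follow-up sentence belongs to Phase 1, where it stands.

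**What to change.** In the Phase 2 Safety and Monitoring text:

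1. Ask Phase 1's question on emotions, motivation or behavior alongside the cognitive question at the planned contacts, at minimum the final one.
2. Date the final contact 5 to 14 days after the last session attended, whether or not later sessions take place, for subjects who still permit contact. Count a session of any condition, because Phase 2 includes sham and same-frequency stimulation without assigning them to sessions.
3. State that the contact form completed in all phases may be used for safety follow-up. Its stated uses are payment and future studies.

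The cost is a few extra questions at contacts already planned and one short call for each early stopper. No visits, stimulation or subjects are added.

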#### **Safety and Monitoring:**

- 1. Comfort:** Subjects will be asked to rate (1-5 scale) severity, location and quality (self described) of any discomfort using the attached stimulation experience scale immediately prior to the stimulation, immediately after each 10 minute stimulation block, and at 10 minutes after the stimulation session. If any discomfort persists at 10 minutes after stimulation, treatment and ongoing assessment will be arranged as needed by the study physician.
- 2. Cognitive Effects:** Baseline memory, attention and verbal reasoning will be assessed using the Digits span test from the WASI, which assesses short-term memory and attention. This will be repeated 10 minutes after the stimulation. Subjects will also be asked open ended questions about any changes in their thinking or cognitive status.
- 3. Psychiatric Effects:** Emotional, motivational and behavioral symptoms will be assessed using the PANAS (Positive and Negative Affect Scale) before stimulation and immediately following stimulation.
- 4. COVID-19 safety:** Subject and experimenter, both wearing masks, enter the testing room. Experimenter places electrodes on subject's head and adjusts them. Experimenter gives the subject an e-cigarette mouthpiece and an exhaust device to exhale into (which has a carbon and HEPA filter to filter the subject's exhaled breath and nicotine vapor), with instructions for the subject to remove their facemask after the experimenter has left the room, inhale from the e-cigarette per protocol, and exhale into the exhaust device. Experimenter leaves the room, after which subject removes their own facemask. Subject proceeds to do the experiment and puts their facemask back on before the experimenter again enters the room.

**Phase 4. Relative effectiveness of stimulation.** In phase 4, we will compare TI-NDBS vs.

conventional transcranial direct current stimulation for smoking reduction. To test this, we will recruit another group of subjects who are heavy smokers into three groups, then ask them to abstain from smoking. Prior to stimulation, subjects will be given the NDSS to determine baseline nicotine dependence. The first group will receive standard transcranial direct current anodal stimulation of the right DLPFC and cathodal stimulation of the left DLPFC (F3 and F4 in the 10/20 system). The second group will receive TI-NDBS to either the nucleus accumbens or anterior insula or anterior cingulate, depending on which is found to be more effective in Phase 3. The third condition will be sham. The strength of the stimulation and duration will be the same as in previous phases. Prior to stimulation, subjects will be administered a questionnaire to assess their physical experiences and sensations using a 5-point Likert-Scale. Immediately after stimulation, subjects will complete the stimulation experience scale, then complete the scale again 30 minutes later. In addition, we will assess craving levels every 10 minutes during the stimulation period. We will repeat this for five consecutive days. We will then follow up with subjects every day, up to three times per day, for 1 week after starting the tDCS, using EMA via a free smartphone app (ilumivu.com) to monitor cigarette use and craving. The questions that will be used in the app are in a script attached (see EMA follow up questions). We will compare the sham vs. tDCS vs. TI-NDBS groups to identify differences in craving and relapse. We expect to find that TI-NDBS leads to reduced craving and drug use relative to sham or tDCS. The procedure in this phase will not add anything new, except testing subjects with tDCS in addition to TI-NDBS and sham.

#### Safety and Monitoring:

1. **Comfort:** Subjects will be asked to verbally rate (1-5 scale) severity, location and quality (self described) of any discomfort immediately prior to the scan, after each block during the scan, immediately after the stimulation session and at 10 minutes after the stimulation session. If any discomfort persists at 10 minutes after stimulation, treatment and ongoing assessment will be arranged as needed by the study physician.
2. **Cognitive Effects:** Baseline memory, attention and verbal reasoning will be assessed using the Digits span test from the WASI, which assesses short-term memory and attention. This will be repeated 10 minutes after the stimulation. Subjects will also be asked open ended questions about any changes in their thinking or cognitive status.
3. **Psychiatric Effects:** Emotional, motivational and behavioral symptoms will be assessed using the PANAS (Positive and Negative Affect Scale) before stimulation and immediately following stimulation.

#### New technology.

Temporally-interfering non-invasive deep brain stimulation (TI-NDBS) is a form of transcranial alternating current stimulation (tACS) which allows focal stimulation and disruption of deep brain structures, without invasive measures, and without disrupting overlying brain regions (Grossman et al., 2017, Cell). Temporal interference tACS (TI-NDBS) has been used since at least the 1970s in humans to treat pain, and devices and software to stimulate the human brain with temporal interference tACS is now FDA approved for investigational use and sold commercially <https://soterixmedical.com/research/interferential-stimulation>.

TI-NDBS works by applying two or more alternating current electric fields to the scalp at frequencies above those necessary to cause stimulation (e.g. 2KHz). The field frequencies differ by a small amount (e.g. 2000 Hz vs. 2010 Hz), so that the differences causes a 10 Hz beat frequency where the fields overlap, similar to the beat frequency of two guitar strings which are slightly out of tune with each other. The location can be tuned to anywhere in the brain, and with any beat frequency, even within deep structures (Figure 1, from Grossman et al., 2017). In our study, subjects will also receive stimulation from all electrodes at the same

Indiana University, Bloomington, IN

frequency (e.g. 2000 Hz) in order to make comparisons to temporal interference stimulation (e.g. 2000 Hz vs. 2010 Hz).

As the technology is very new, we do not yet have sufficient data to estimate an effect size of TI-NDBS on nicotine or opiate use or craving. We specifically hypothesize that tDCS neurostimulation to the dorsolateral PFC will reduce nicotine intake and craving, and that TI-NDBS to the insula will be more effective than tDCS at reducing both nicotine intake and craving. The electrodes will be placed according to the standard EEG 10/20 system.

For tDCS to the dorsolateral prefrontal cortex, we will place electrodes over F3 and F4. For TI-NDBS, we will use finite element methods ([simnibs.org](http://simnibs.org) or [sim4life](http://sim4life)) to determine where to place each of four electrodes (two pairs) in order to target the desired brain region. Each smoking subject will be allowed *ad lib* intake from our custom e-cigarette, which measures total inhaled vapor and thus nicotine intake (as we verified in Velez et al., 2015). As a measure of short-term neurostimulation effectiveness, we will compare total nicotine inhaled during stimulation for tDCS, TI-NDBS, and sham subjects. We will also ask for periodic self reports of craving during stimulation, i.e. “How much do you want to smoke?”, on a Likert scale of 0-10. We will compare self-reported craving across different stimulation conditions. For long-term assessment, we will use ecological momentary assessment, with the [Illumivu.com](http://Illumivu.com) system. Subjects will be prompted 3 times a day (morning, afternoon, and evening) between neurostimulation sessions and for the next two weeks following neurostimulation to report how many cigarettes they smoked in the preceding time period, and how much they are craving cigarettes at the moment. We will use this information to assess how strong the effect of stimulation is even after the stimulation session has ended. In the lab, we will measure recent smoking by measuring breath carbon monoxide (CO, Smokerlyzer PiCO).

[figure not shown]

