### **TI device**

The TI device was custom-built by the machine shop in the department of Psychological and Brain Sciences based off of schematics that [name] (PI) and [name] (Ph.D., electrical engineer) devised based on the work of Grossman et al. 2017 (for device images and circuitboard diagram see the Notes & Attachments). The TI device contains a mechanism that constantly monitors the amount of current administered via the electrodes. The current study design is single-blind such that the experimenter will become aware of the amount of current administered to ensure the safety of experimental subjects. A prototype of the device is shown in Figure 2. The device has the following characteristics:

- The device is powered by standard 9-volt batteries that provides the energy to carry out the neurostimulation. The device may also be powered by a standard 9-volt power supply.
- There are two electrode pairs, with a total of 4 electrodes, that will connect from the device in Figure 2 to gel electrodes on the subject's head (as shown in Figure 1), typically of varying shapes approximately 2 cm x 2 cm. At 2 mA current, this will result in a maximum current density of  $0.0005 \text{ A/cm}^2$ . At 50Kohm scalp impedance, the total power dissipated by an electrode pair is  $I^2R = 200 \text{ mW}$ , which is comparable to the power emitted by a cell phone.
- Each electrode pair generates a sinewave alternating current, with no DC component. The frequency can be varied continuously from zero to over 5 Khz. We will not apply alternating current frequencies over 5Khz. Typically, the frequencies will be around 2 Khz.

- The frequency difference between the electrodes will be varied between 1-100 Hz.
- The current for each electrode pair can be controlled continuously from zero to 2 mA. Each of the two electrode pairs may have a different current level, which allows the focal point of stimulation in the brain to be steered without moving the electrodes.
- For safety, the device includes an onboard current monitor to measure the amount of current actually delivered. The device can be powered down if for any reason the amount of current exceeds the specified setting, or if the voltage required to deliver the current exceeds the device's capacity.

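### Phase 4 has two active arms with different electrode layouts and one sham of unstated layout, so as written at most one sham comparison is matched for set-up

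*Combined protocol and SAP*

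**What the plan says.** Section 3.0 (Phase 4) and section 6.0 describe three groups of 15 heavy smokers: tDCS over the dorsolateral prefrontal cortex, TI-NDBS to the best site from Phase 3, and sham. Sessions are repeated on five consecutive days.

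- **tDCS layout** (3.0, New technology): "For tDCS to the dorsolateral prefrontal cortex, we will place electrodes over F3 and F4". One site is anodal and the other cathodal.
- **TI-NDBS layout**: field modelling is used "to determine where to place each of four electrodes (two pairs") should go. The TI device section confirms the count: "There are two electrode pairs, with a total of 4 electrodes".
- **Phase 4 sham**: "The third condition will be sham". Nothing more is said about its electrodes or waveform.
- **The only description of a sham current** is under Phase 2: "For sham stimulation, the current will increase during a 30 second interval and then immediately decrease back to zero over a 30 second interval". It does not cover electrode number or position.
- **Phase 4 relative to earlier phases**: "The procedure in this phase will not add anything new, except testing subjects with tDCS in addition to TI-NDBS and sham".
- **Masking** (TI device): "The current study design is single-blind such that the experimenter will become aware of the amount of current administered".
- **Waveform of the TI device**: "Each electrode pair generates a sinewave alternating current, with no DC component".

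Phase 4 outcomes include craving reported every 10 minutes during stimulation, and craving and cigarette use reported by smartphone. Section 3.0 (New technology) also compares device-measured inhaled nicotine across tDCS, TI-NDBS and sham, and plans breath carbon monoxide as a measure of recent smoking.

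**The concern.** A sham arm protects a comparison only if the sham set-up resembles the active set-up it is compared with. Here the two active set-ups differ in the number and position of electrodes, and there is one sham.

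The experimenter knows the current, so the subject is the only party the plan describes as masked, and several Phase 4 outcomes are the subject's own ratings. If the set-up affects what a subject expects, that expectation is mixed into whichever contrast is unmatched. TI-NDBS versus tDCS, which the Specific Aim leads up to, is unmatched whatever the sham looks like.

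Phase 4 is meant to estimate effect sizes from 45 subjects. A bias of this kind goes straight into the estimate, and enrolling more subjects does not remove it.

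**Working it through.** **1. The plan's own figure.** Three groups of 15 give 3 × 15 = 45, as section 6.0 states. The plan gives no alpha, power, effect size or SD for Phase 4, so there is no power figure to reproduce.

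**2. Which contrasts can be matched for set-up.** This assumes that tDCS subjects wear electrodes only at F3 and F4 and TI-NDBS subjects wear only the four modelled electrodes. The text implies this without stating it.

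| Sham layout | tDCS vs sham | TI-NDBS vs sham | TI-NDBS vs tDCS |
|---|---|---|---|
| F3/F4 only | matched | not matched | not matched |
| Four TI positions | not matched | matched | not matched |
| Any other single layout | not matched | not matched | not matched |
| Same full layout on every subject in all arms (not described) | matched | matched | matched |

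Under the first three rows at most one of the three contrasts is matched. Only the last row matches all three. Simply writing down which single layout the sham uses would not resolve the problem.

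**3. Waveform and sensation.** The TI device has no DC component, so as described it does not deliver tDCS. The Background reports mild skin irritation with tDCS but not with tACS. The active arms may therefore feel different even under identical electrodes, and the waveform of the sham ramp is unspecified.

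**4. Illustration of size.** The documents give no size for an expectation effect, so the shift is an assumption, shown over a range. Inputs: n = 15 per arm (section 6.0), two-sided alpha 0.05 (assumed), two-sample t-test with 15 + 15 − 2 = 28 degrees of freedom, no true effect, and a mean shift of δ SD from expectation alone. The noncentrality is δ × √(15/2) = 2.739 δ.

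| Assumed shift δ (SD) | Noncentrality | Chance of rejection |
|---|---|---|
| 0 | 0 | 5.0% |
| 0.2 | 0.548 | 8.3% |
| 0.3 | 0.822 | 12.5% |
| 0.5 | 1.369 | 26.2% |

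For scale, the one effect size quoted in section 3.0 is d = 0.71, for reduced cigarette consumption after five days of tDCS. Shifts of 0.3 and 0.5 SD would be 0.3/0.71 = 42% and 0.5/0.71 = 70% of it, though that figure concerns a different measure from craving.

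**5. Precision if the sham group is split.** With 15 per arm, the standard error of a mean difference is √(1/15 + 1/15) = 0.365 SD. Against a matched sham half of 8 it is √(1/15 + 1/8) = 0.438 SD, and against 7 it is √(1/15 + 1/7) = 0.458 SD. These are 20% and 25% larger.

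**The case against.** A reader might infer that one sham can never resemble both active arms. The documents do not support that. They are silent on the sham layout, the two-electrode count for tDCS is inferred, and a common layout would let one sham match both. The limitation belongs to the design as written.

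A reader might also infer that subjects will recognise their assignment. That is not shown. The groups are parallel, so each subject sees one set-up and has nothing to compare it with. What subjects are told about the arms is not in the reviewed text. This objection stands, and it is why the bias is stated only as possible. It does not remove the mismatch: even if nobody guesses, set-up and treatment differ together in the unmatched contrasts.

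Subject masking is not the only safeguard. In Phase 3 the experimenter leaves the room before inhalation starts, and Phase 4 is said to add only tDCS. Follow-up reports are entered in an app. Inhaled nicotine is measured by the device, and breath carbon monoxide does not depend on a rating. These measures reduce the exposure, although ad lib intake is voluntary and can still respond to expectation.

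Finally, for TI-NDBS versus tDCS even the direction of an expectation shift is unknown, and Phase 4 is framed as estimation. Both points stand. The main consequence is possible bias in the estimates, and the rejection rates above are illustrative.

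**Conclusion.** The concern holds for Phase 4 as written. One sham set-up can match at most one active arm, TI-NDBS versus tDCS is not matched for set-up, and no check of subjects' beliefs about assignment is described. This rests on reading the layouts as two electrodes for tDCS and four for TI-NDBS, with no common layout.

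The outcomes most exposed are self-reported craving and cigarette use. Ad lib nicotine intake is possibly affected. Device-measured inhalation and breath carbon monoxide are less exposed as measurements. The size of any bias is unknown. The range of 8.3% to 26.2% follows from assumed shifts of 0.2 to 0.5 SD and should not be read as the trial's error rate.

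The change is worth making before Phase 4 starts, because a mismatch in set-up cannot be corrected in the analysis.

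**What to change.** - **Preferred.** Where the modelled TI positions allow, place one common layout (F3/F4 plus the TI positions) on every Phase 4 subject and energise only the assigned electrodes. Deliver the sham ramp through the same layout, and state its waveform and which electrodes carry it.
- **If the TI positions overlap or abut F3/F4.** Split the sham group between the tDCS and TI layouts, 7 and 8 subjects. Compare each active arm with the whole sham group and report the comparison with the matched half beside it. This is weaker: the matched-half comparison has a standard error 20% to 25% larger, and TI-NDBS versus tDCS stays unmatched.
- **In either case.** Add one item to the stimulation experience scale asking which condition the subject believes they received, and report it by arm. This is needed because a common layout will not hide sensation differences between alternating and direct current.

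The cost is some extra set-up time per session, possibly a check in the field model of the effect of idle electrodes, and one questionnaire item. No extra subjects or staff are needed.
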